6.1 Sample Size Estimation

6.1.1 Cigarette consumption

An intended sample size of 50 subjects in each of the two groups who switch from smoking usual brand to VLN cigarettes has been set for this study. This is based on powering the primary objective of a within-group comparison of cigarette consumption at baseline and end-of-study. The calculation was based on the number of pairs required to perform a two-tailed paired t-test with 80% power and an alpha level of 0.05 for a decrease in cigarette consumption of 3 CPD compared to available historical consumption data (2, 4). The sample size was determined to be adequate based on potential non-compliance with the use of VLN cigarettes (2). A lower number (20) of smokers will be randomized to the continue-to-smoke usual brand groups, given the lower variability in consumption data and lower non-compliance anticipated in these groups. This will provide sufficient power for the secondary objective of between-group comparisons in cigarette consumption.

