7.3 Statistical Analysis of Primary Endpoints

Paired t-tests will be used to compare cigarette consumption (CPD) and puffing topography parameters at the Week 2 and Week 6 time points with the baseline (Week -1) values. This analysis will be conducted on the evaluable subjects in the PP population. If data are unexpectedly found not to be normally distributed, an appropriate non-parametric test will be performed. Differences will be considered statistically significant at an alpha level of 0.05. Means, difference of means, 90% confidence interval for difference, and p-value will be presented.

The following SAS codes will be used for the analysis:

```
Proc ttest data=<>;  
By product_group;  
Paired week_X*baseline;  
Run;
```

Where week_X will be either Week 2 or Week 6. Product Groups are VLN non-mentholated, VLN non-mentholated, and VLN combined which pooled non-mentholated and mentholated groups. The primary analysis will be based on the VLN combined product group.

In addition, a linear mixed model analysis of variance will be used to compare the between product group differences in the absolute change from baseline values of the consumption and puffing topography parameters. Product group, week, and product group by week interaction will be the fixed factors in the model. A restricted maximum likelihood estimation method with an unstructured (UN) covariance structure will be applied. If the model does not converge, the first order autoregressive AR(1) and/or compound symmetry CS covariance structures will be tested as alternatives. The least-square mean difference, 95% confidence interval and p-value will be provided for the product group difference. The pairwise comparisons (VLN non-mentholated versus UB non-mentholated, VLN mentholated versus UB mentholated, and VLN combined versus UB combined) will be performed at week Week 2 and Week 6. Least-square means (LSMeans), difference of LSMeans, 90% confidence interval for difference, and p-value for difference will be presented.

The following SAS codes will be used to perform the analysis.

```
Proc mixed data=<>;  
Class subject product_group week;  
Model response = product_group week product_group*week /ddf=kr;  
Repeated week/type=<type> subject=subject;  
LSmeans product_group*week/CL alpha=0.05 CL pdiff;  
Run;
```

The primary analysis will be the pairwise comparisons of VLN combined versus UB combined (pooled non-mentholated and mentholated groups).

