8.4 Statistical Analysis of Biomarkers of Exposure

Paired t-tests will be used to compare urinary NNAL, NNN, 3-HPMA, S-PMA, 1-OHP, Tneq mass excreted, and blood COHb measures at the Week 2 and 6 time points with the baseline (Week -1) values. This analysis will be conducted on the evaluable subjects in the PP population. If data are unexpectedly found not to be normally distributed, an appropriate non-parametric test will be performed.

Differences will be considered statistically significant at an alpha level of 0.05. The same SAS codes used in [Section 7.3](#) for paired t-test will be used for the analysis.

In addition, a linear mixed model analysis of variance will be used to compare the between product group differences in the absolute change from baseline values of each of the urinary and blood BoEs. The same statistical model and SAS codes used in [Section 7.3](#) for product group comparisons will be used for the analysis.

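### SAP 7.3 shares one covariance matrix between VLN and UB; if UB is less variable, as the sample size section expects, the VLN-versus-UB standard errors for CPD are too wide

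*SAP*

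**What the plan says.** SAP 7.3 adds to the paired t-tests a linear mixed model to "compare the between product group differences in the absolute change from baseline values of the consumption and puffing topography parameters". The fixed effects are product group, week and their interaction. On the covariance it says: "A restricted maximum likelihood estimation method with an unstructured (UN) covariance structure will be applied". The code line is "Repeated week/type=<type> subject=subject", with Kenward-Roger degrees of freedom requested in the MODEL statement. The fallback is: "If the model does not converge, the first order autoregressive AR(1) and/or compound symmetry CS covariance structures will be tested as alternatives". Neither document provides for variances that differ between product groups.

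On the contrast that matters most, SAP 7.3 says: "The primary analysis will be the pairwise comparisons of VLN combined versus UB combined (pooled non-mentholated and mentholated groups".

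Protocol 6.1.1 explains the allocation: "A lower number (20) of smokers will be randomized to the continue-to-smoke usual brand groups, given the lower variability in consumption data". Lower expected non-compliance is the second reason given, and SAP 4.1 repeats both. SAP 8.4 carries the model over to the biomarkers: "The same statistical model and SAS codes used in [Section 7.3](#) for product group comparisons will be used for the analysis". SAP 10.3 makes the same cross-reference in the subjective effects section.

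**The concern.** Unstructured here means unstructured across weeks. Without GROUP=, the week-by-week matrix is the same for every product group, and so are the AR(1) and CS fallbacks. Kenward-Roger works on that same common matrix and does not correct for unequal group variances.

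The design and the model therefore rest on different assumptions. The allocation relies on UB being less variable, while the model takes UB to be exactly as variable as VLN. With more VLN than UB subjects, the pooled variance lies close to the VLN variance and is then applied to the small UB groups. If the stated expectation is right, the precision that was meant to excuse the small control groups does not reach the reported intervals. This is the trial's only comparison with concurrent controls, and both documents claim sufficient power for it without giving a figure.

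**Working it through.** **Inputs.** Planned sizes are 50 VLN and 20 UB per flavour, so 100 v 40 combined (Protocol 6.1.1, SAP 4.1). The response is change from baseline (SAP 7.3). The reported comparison uses the per-protocol (PP) population (SAP 13.2, Table 14.2.1.1.3). The effect of 3 CPD, 80% power and alpha 0.05 come from the sample size sections, where 3 CPD is a within-group decrease. The UB/VLN SD ratio r is not given, so 0.5 to 1.0 is assumed. Complete data are also assumed.

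**The plan's own figure.** The 50 per flavour cannot be reproduced, because no SD is stated. Solving backwards for a paired t-test with 50 pairs and 3 CPD gives an SD of change of 7.42 two-sided (Protocol) or 8.41 one-sided (SAP), before any allowance for non-compliance. The two-sided normal approximation is 3√50/(1.96 + 0.84) = 7.57. The power illustration below assumes a VLN SD of 7.4.

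**Standard error.** With a group-by-week mean model and complete data, the common-matrix REML variance at a given week is the pooled within-group variance. Take the VLN SD as 1. The degrees of freedom are 98 for VLN (two groups of 50) and 38 for UB (two groups of 20).

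- Pooled variance: s² = (98 + 38r²)/136
- Variance as modelled: s²(1/100 + 1/40)
- True variance: 1/100 + r²/40
- SE ratio: square root of modelled over true

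At r = 0.8, s² = (98 + 24.32)/136 = 0.8994. The modelled variance is 0.8994 × 0.035 = 0.03148, and the true variance is 0.010 + 0.016 = 0.026. The SE ratio is √(0.03148/0.026) = 1.10.

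The actual two-sided error is about 2(1 − Φ(1.96 × SE ratio)).

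| r (UB/VLN SD) | SE ratio, 100 v 40 | Actual error at nominal 5% | Coverage of nominal 90% interval |
|---|---|---|---|
| 1.0 | 1.00 | 5.0% | 90.0% |
| 0.9 | 1.05 | 4.0% | 91.5% |
| 0.8 | 1.10 | 3.1% | 93.0% |
| 0.7 | 1.16 | 2.3% | 94.4% |
| 0.6 | 1.23 | 1.6% | 95.7% |
| 0.5 | 1.30 | 1.0% | 96.8% |

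A simulation with four groups of 50, 50, 20 and 20 (8,000 runs per setting) gave SE ratios of 1.10, 1.15 and 1.30 at r = 0.8, 0.7 and 0.5. Group-specific variances gave ratios of 0.99 to 1.00 and a two-sided error of 0.048 to 0.054.

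**Power, for illustration.** At r = 0.8 and VLN SD 7.4, the true SE is 7.4 × √0.026 = 1.193, and 3/1.193 = 2.514. With the common matrix (136 df, critical value 1.978), power is Φ(2.514 − 1.978 × 1.100) = Φ(0.338) = 63%. With separate variances (Satterthwaite df about 87, critical value 1.988), it is Φ(2.514 − 1.988) = Φ(0.526) = 70%.

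**Sensitivity to the analysed numbers.** No exclusion rate is given, so these sizes are assumed.

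- 60 v 38: SE 2% and 5% too wide at r = 0.9 and 0.8; 11% and 15% at r = 0.6 and 0.5.
- 40 v 38: under 2% too wide at every r from 0.5 to 1.0.
- 24 v 36 (12 v 18 per flavour), r = 0.7: SE ratio 0.93, simulated error about 7%.
- 100 v 40 with UB the more variable group, r = 1.25: SE ratio 0.91, error about 7%.

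**The case against.** The case against giving this much weight is substantial, and most of it stands.

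- **Direction.** A reader might infer that the reported p-values could produce false positives. At the planned sizes and under the plan's own expectation, the test is conservative, and the loss is power only.
- **Certainty.** A reader might say the standard errors are simply wrong as written. The documents give only a qualitative expectation about consumption data, with no SD, and do not say whether it concerns CPD level or change from baseline, which is what is modelled. Lower non-compliance is a separate reason for the 20. At equal variances there is no error.
- **Population.** The comparison uses the PP set. The cotinine-ratio rule in SAP 5 can remove VLN subjects, which shrinks the bias and may also alter VLN variability.
- **Status.** SAP 7.3 attaches the word primary to the combined contrast, but Protocol 6.1.1 and SAP 4.1 call the between-group comparison of consumption a secondary objective. The SAP wording may only pick one of three contrasts. The powered within-group paired t-test is unaffected.
- **Biomarkers.** It is tempting to add that forced switching makes VLN biomarker change more variable than UB change. Nothing in the documents says so. The order would depend on within-subject correlations that are not given.
- **Power figures.** These depend on treating all 50 as evaluable pairs, and no between-group effect is stated.

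What does not stand is that a common matrix is a harmless default. Whether it is conservative depends on group sizes after exclusions and on a variance ratio that nobody has stated.

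**Conclusion.** The point holds in conditional form for the CPD comparison. The model ignores a variance difference that the plan itself offers as part of the reason for small UB groups. If UB change is less variable, the VLN-versus-UB standard errors at 100 v 40 are too wide by about 5% at an SD ratio of 0.9, rising to 30% at 0.5, with a matching loss of power and no inflation of type I error. The ratio is an assumption throughout. Smaller analysed VLN numbers reduce the error, and it changes sign if VLN becomes the smaller group or UB proves the more variable. The documents do not support a claim of invalid results, nor any statement about which arm is more variable for biomarkers or subjective scores. This is a worthwhile, inexpensive correction and not a must-fix.

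**What to change.** In SAP 7.3, derive a two-level variable `arm` (VLN or UB), add it to the CLASS statement, and change the REPEATED statement to

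`repeated week / type=un subject=subject group=arm;`

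Keep Kenward-Roger, and carry the same GROUP= option into the AR(1) and CS fallbacks. Apply this to the CPD comparison. Apply it also to the models that reuse the code under SAP 8.4 and 10.3, as protection against unequal variances in either direction, without asserting which arm is more variable there. Exclude topography: SAP 7.1.3 restricts that subset to subjects assigned to VLN, so a UB matrix and a VLN-versus-UB contrast cannot be estimated. It would also help to state the SD assumed for each arm behind the sufficient-power claim in SAP 4.1.

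The change should be fixed in the SAP before the data are seen. With Weeks 2 and 6 in the model, it adds one 2 × 2 matrix, that is three covariance parameters (more if further weeks are modelled). If the variances are in fact equal, the combined contrast loses under 1 point of power.

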2.1 Design and Procedures

This is an open-label, non-randomized, forced-switching study to be conducted at multiple study sites. Seventy (70) self-affirmed exclusive filtered king size non-mentholated cigarette smokers and 70 self-affirmed exclusive filtered king size mentholated cigarette smokers will be enrolled and begin the study at Week -1.

All potential subjects will provide informed consent and successfully complete the Screening procedures prior to participation in the study. Subjects will also engage in a brief product trial with the VLN cigarettes. Subjects who react negatively (i.e., unwilling to use and/or cannot tolerate the product [experience adverse events (AEs) that will prevent them from continuing to use the product as judged by the Investigator]) to the VLN cigarettes during the product trial period will not continue in the study.

At the start of Week -1, all subjects will be asked to smoke their UB cigarettes as per their usual daily consumption for the following week. Subjects will receive an electronic diary (e-diary) to record daily cigarette use (cigarettes per day [CPD]). Training in completion of the e-diary will be provided at the visit at the start of Week -1.

Subjects will return at the end of Week -1, at the time indicated by the clinical research unit (CRU), for collection of blood and 24-hour urine samples for baseline BoE assessments. Subjective questionnaires for dependence, withdrawal symptoms, urges to smoke, and perceived health risk will also be completed at scheduled times. A subset of 18 non-menthol and 18 menthol smoker subjects will complete an assessment of puffing topography with their UB cigarettes during this visit. A further subset of 12 of the non-menthol and 12 of the menthol smoker subjects who complete the topography assessment will also complete a nicotine PK assessment at the end of this visit. Subjects who undergo topography and PK assessments will be assigned to switch to smoking VLN cigarettes.

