3. STUDY DESIGN

This is an open-label, randomized, forced-switching study to be conducted at multiple study sites. Seventy (70) self-affirmed exclusive filtered non-mentholated cigarette smokers and 70 self-affirmed exclusive filtered mentholated cigarette smokers will be enrolled and begin the study at Week -1.

All potential subjects will provide informed consent and successfully complete the Screening procedures prior to participation in the study. Subjects will also engage in a

brief product trial with the VLN cigarettes. Subjects who react negatively (i.e., unwilling to use and/or cannot tolerate the product [experience AEs that will prevent them from continuing to use the product as judged by the Investigator]) to the VLN cigarettes during the product trial period will not continue in the study.

At the start of Week -1, all subjects will be asked to smoke their UB cigarettes as per their usual daily consumption for the following week. Subjects will receive an e-diary to record daily cigarette use (CPD). Training in completion of the e-diary will be provided at the visit at the start of Week -1.

Subjects will return at the end of Week -1, at the time indicated by the clinical research unit (CRU), for collection of blood and 24-hour urine samples for baseline BoE assessments. Subjective questionnaires for dependence, withdrawal symptoms, urges to smoke, and perceived health risk will also be completed at scheduled times. A randomly-selected subset of 18 non-menthol and 18 menthol smoker subjects will complete an assessment of puffing topography with their UB cigarettes during this visit. A further subset of 12 of the non-menthol and 12 of the menthol smoker subjects who complete the topography assessment will also complete a nicotine PK assessment at the end of this visit. Subjects who undergo topography and PK assessments will be assigned to switch to smoking VLN cigarettes.

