On Day -1 of Week 1, subjects will be randomly selected to either remain smoking their non-menthol (20 subjects) or menthol (20 subjects) UB cigarettes, or to switch to smoking non-menthol (50 subjects) or menthol (50 subjects) VLN cigarettes as per their UB cigarette flavor. Subjects will return at the end of Weeks 2 and 6, at the time indicated by the CRU, for collection of blood and 24-hour urine samples for BoE assessments. Subjective effects questionnaires will also be completed at scheduled times. Subjects will continue recording their CPD in their e-diaries. The same subset of 18 non-menthol and 18 menthol smoker subjects selected to complete a puffing topography assessment with their UB cigarette on Week-1, will complete an assessment of puffing topography with the VLN cigarettes at these visits, and a further subset of 12 non-menthol and 12 menthol smoker subjects will also complete an assessment of nicotine PK at the end of these visits. Subjects undergoing topography and PK assessments will have been assigned to switch to smoking VLN cigarettes.

Additionally, all subjects will visit the clinic at the end of Week 4 to receive further supplies of cigarettes (if assigned to the VLN groups) and to complete subjective effects questionnaires.

Subjects randomized to the VLN groups will be provided with a supply of VLN cigarettes at each visit, which will be 150 % of their usual daily consumption as reported during Week 1. If a subject runs out of cigarettes between clinic visits, they may visit the clinic to receive additional test cigarettes. All subjects will be asked to smoke their cigarettes *ad libitum*, recording their actual daily consumption in their e-diaries. Non-compliant nicotine product consumption should also be recorded. Used

cigarette butts will also be collected during ambulatory periods to verify product use and/or assess compliance. During Week 1 (all subjects) and all subsequent weeks (subjects randomized to continue smoking UB cigarettes) subjects will be asked not to change their UB cigarette brand or flavor.

The CRU will attempt to contact all subjects who participated in the study (including subjects who terminate the study early) using their standard procedures approximately 7 days after the last contact to determine if any AE has occurred since the last study visit.

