5. ANALYSIS POPULATIONS

The statistical analysis will be based on separate, hierarchically organized, analysis populations defined as the following:

Safety population: All enrolled subjects who smoked at least one cigarette of any type. This population will be used for safety analysis.

Intent-to-treat (ITT) population: All subjects who had at least one valid recording of cigarette consumption (a period of one week of >70% completion of their e-diary).

Per-protocol (PP) population: All subjects who had valid recording of cigarette consumption and completed the study according to the protocol. Data will be excluded from this population:

- If a subject self-reports smoking a significant number of cigarettes other than those which they have been assigned according to the protocol, or if this is apparent following checking of their collected used cigarette butts
- If there is a significant discrepancy between the self-reported number of cigarettes smoked per day and the number of used cigarette butts collected
- If a subject is non-compliant based on a published method of assessing compliance. After switching, subjects will be deemed non-compliant if their ratio of [plasma cotinine/CPD VLN]/[plasma cotinine/CPD baseline] exceeds 0.2.

If it is determined that a subject is pregnant during the study, the pregnant subject's data will be listed but excluded from all PK parameter summaries.

PK Population: Subjects in the PP or ITT population who have at least one PK blood draw resulting in at least one quantifiable plasma nicotine concentration. This population will be used for PK analysis (secondary endpoint analysis) and all available data will be included in the concentration and PK parameter tables to the extent possible.

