14.2 Pharmacokinetic and Pharmacodynamic Data Summary Tables and Figures

14.2.1 Product Use Tables

Table 14.2.1.1.1.1 Summary of Number of Cigarettes Smoked per Week by Study Product Group and Study Week (PP Population)

Table 14.2.1.1.1.2 Summary of Number of Cigarettes Smoked per Week by Study Product Group and Study Week (ITT Population)

Table 14.2.1.1.2 Statistical Comparison of Number of Cigarettes Smoked per Week at Weeks 2 and 6 Versus Week -1 by Study Product Group (PP Population)

Table 14.2.1.1.3 Statistical Comparison of Number of Cigarettes Smoked per Week Among Study Product Groups at Weeks 2 and 6 (PP Population)

Table 14.2.1.2.1.1 Summary of Number of Cigarette Butts Collected per Week by Study Product Group and Study Week (PP Population)

Table 14.2.1.2.1.2 Summary of Number of Cigarette Butts Collected per Week by Study Product Group and Study Week (ITT Population)

Table 14.2.1.2.2 Statistical Comparison of Number of Cigarette Butts Collected per Week at Weeks 2 and 6 Versus Week -1 by Study Product Group (PP Population)

Table 14.2.1.2.3 Statistical Comparison of Number of Cigarette Butts Collected per Week Among Study Product Groups at Weeks 2 and 6 (PP Population)

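### Every planned VLN versus UB test is on the per-protocol set, one of whose rules can remove only VLN subjects, and no ITT test or interval is planned beside it

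*SAP*

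**What the plan says.** **Tests.** SAP 7.3, 8.4 and 10.3 put the paired tests on PP by text, and SAP 9.5 uses the PK population drawn from PP. For the paired CPD and topography tests SAP 7.3 adds: "The primary analysis will be based on the VLN combined product group". It then describes a mixed model for VLN versus UB and closes with: "The primary analysis will be the pairwise comparisons of VLN combined versus UB combined (pooled non-mentholated and mentholated groups". The mixed-model paragraphs name no population. The table titles do, for example "Table 14.2.1.1.3 Statistical Comparison of Number of Cigarettes Smoked per Week Among Study Product Groups at Weeks 2 and 6 (PP Population").

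**ITT.** This population (SAP 5: at least one week with more than 70% diary completion) is used for descriptive output, for example "Table 14.2.1.1.1.2 Summary of Number of Cigarettes Smoked per Week by Study Product Group and Study Week (ITT Population").

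**PP.** SAP 5 lists completion according to the protocol and three grounds for exclusion: substantial smoking of non-assigned cigarettes, a substantial mismatch between diary and butt count, and a biochemical rule taken from a published method: "After switching, subjects will be deemed non-compliant if their ratio of [plasma cotinine/CPD VLN]/[plasma cotinine/CPD baseline] exceeds 0.2".

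**Allocation.** SAP 3 says that "subjects will be randomly selected to either remain smoking their non-menthol (20 subjects) or menthol (20 subjects) UB cigarettes" or to switch (50 and 50). Protocol 6.1.1 and SAP 4.1 anticipate lower non-compliance in the UB groups.

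**The concern.** The biochemical rule depends on what subjects do after allocation, and it can shrink only one arm. A VLN versus UB difference computed after it compares the UB group with a screened subset of the VLN group. SAP 7.3 calls that contrast primary, yet no planned analysis would show whether the answer depends on the screening.

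Two features sharpen this. The rule contains an outcome, because CPD on VLN is in a denominator. It also uses plasma cotinine, while total nicotine equivalents (Tneq, SAP 8.1.3) sum nicotine, cotinine and related metabolites. Selecting on one nicotine biomarker may therefore carry into the estimated reduction of another.

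**Working it through.** The plan gives no non-compliance rate and no SD of change, so there is no figure of its own to reproduce. The check has four parts.

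**1. Population of each comparison table (SAP 13.1 and 13.2).** Section 14 lists 29 statistical comparison tables: product use 4, topography 2, biomarkers 14 (7 markers x 2), PK 1, subjective effects 8. Of these, 28 are titled PP and the PK table is drawn from PP. All 14 in-text comparison tables are PP as well. None is ITT. Fourteen of the 29 are VLN versus UB: 14.2.1.1.3, 14.2.1.2.3, 14.2.3.3, seven numbered 14.2.5.x.3 and four numbered 14.2.9.x.3.

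**2. Which arm the rule can touch.** The ratio needs a post-switch CPD on VLN. A subject who continues on UB has none, so the rule can exclude VLN subjects only. The other PP criteria can remove subjects from either arm.

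**3. What retention implies.** Let r = CPD VLN / CPD baseline. A subject is kept if follow-up cotinine / baseline cotinine <= 0.2 x r, that is, if cotinine falls by at least 1 - 0.2r:

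| r | 0.5 | 0.75 | 1 | 1.25 | 1.5 |
|---|---|---|---|---|---|
| Minimum fall | 90% | 85% | 80% | 75% | 70% |

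Example with assumed values: baseline 20 CPD and 250 ng/mL, follow-up cotinine 30 ng/mL.
- At 20 CPD: (30/20)/(250/20) = 0.12, kept.
- At 10 CPD: (30/10)/(250/20) = 0.24, excluded.
- The switch is at 30/(0.2 x 12.5) = 12 CPD.

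At equal cotinine, the subject who cut down more is the one removed. Continued UB smoking also raises the ratio. Suppose a VLN cigarette yields a fraction y of a UB cigarette's cotinine, and a share f of cigarettes is UB. Exclusion then occurs when f > (0.2 - y)/(1 - y) if CPD VLN means total CPD, or f > (0.2 - y)/(1.2 - y) if it means VLN cigarettes only. At y = 5% (assumed range 2 to 10%) the thresholds are 15.8% (18.4 to 11.1%) and 13.0% (15.3 to 9.1%). The two mechanisms can move the PP mean CPD change in opposite directions.

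**4. Illustration of size.** From the documents: the 0.2 cut-off, the entry rule of at least 10 CPD, and 100 VLN subjects. All else is assumed:
- baseline CPD N(18, 6), floored at 10;
- CPD change with SD 5 and mean -4 in compliers, and -1, -4 or -7 in non-compliers; follow-up CPD floored at 2;
- UB share zero in compliers and uniform 0.1 to 0.9 in non-compliers;
- y lognormal, median 5%, log-SD 0.4; visit log-SD 0.2 for cotinine and 0.3 for Tneq;
- Tneq proportional to CPD x [f(1-c) + (1 - f(1-c))y], where c is the share of UB smoking that clinic confinement removes from the 24-hour urine;
- total CPD in the rule, one follow-up visit, whole-subject exclusion, no dropout.

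| Assumed non-compliance | 20% | 40% | 60% |
|---|---|---|---|
| VLN subjects kept in PP | 81% | 63% | 45% |
| CPD change, PP minus all switched: non-compliers -1 | -0.5 | -1.0 | -1.4 |
| non-compliers -4 | 0 | 0 | 0 |
| non-compliers -7 | +0.5 | +1.0 | +1.4 |
| Tneq fall, PP minus all switched (points): c = 0 | 6 to 9 | 11 to 18 | 17 to 26 |
| c = 0.5 | 3 to 5 | 6 to 9 | 8 to 13 |
| c = 1 (range over all settings) | -0.3 to +0.5 | -0.3 to +0.5 | -0.3 to +0.5 |
| c = 0, UB share 0.02 to 0.3, non-compliers -4 | about 2 | about 3 | about 4 |

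If confinement lowers plasma cotinine as well, c = 0.5 keeps 85/71/57% with gaps of 2 to 4, 5 to 8 and 7 to 10 points, and c = 1 leaves no gap. With the 0.1 to 0.9 share, the Tneq fall is at least 68% in all switched subjects and about 94 to 96% in PP when c acts on urine only.

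**The case against.** The hypothesis concerns smokers who actually switch, and Protocol 6.3.7 and 6.3.8 prespecify PP for the paired tests. That stands: PP is a reasonable lead set for the within-switcher question. It does not extend to VLN versus UB, where an exclusion specific to one arm breaks the comparison of groups as allocated.

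The report will list weekly cigarettes and plasma cotinine by subject (Appendices 16.2.6.1 and 16.2.6.10) and the excluded subjects (16.2.3.x). A reader could see who was removed, but would still have no planned ITT estimate, interval or p-value.

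A reader might infer more than the documents support:
- *That PP flatters VLN on CPD.* No direction is shown; the illustration changes sign with the assumed behaviour of non-compliers.
- *That the Tneq reduction is an artefact.* It is large in every case examined. Urine is collected in confinement, with belongings checked, only VLN cigarettes permitted for the VLN groups, and use tracked (Protocol 4.2, 5.4, 5.9), so the gap may be negligible.
- *That PP as a whole is one-sided.* Only the cotinine rule is.
- *That CPD change is withheld for ITT alone.* No CPD change table is listed for PP either, and Protocol 6.3 plans change summaries where appropriate.
- *That CPD VLN is undefined.* The rule rests on a cited published method that may define it; the SAP does not restate it. SAP 5 also speaks of excluding data, so exclusion might be by visit.

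**Conclusion.** The point holds as a statement about the plan, with high confidence: all 29 Section 14 comparison tables and all 14 in-text ones are on PP, none is on ITT, and one PP criterion can remove only VLN subjects after allocation. For VLN versus UB, the PP status rests on table titles, because the mixed-model text is silent.

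The consequence is much less certain. Neither the direction nor the size of any CPD bias can be determined from the documents. For Tneq, the size of the PP reduction, not its existence, may partly reflect the inclusion rule. The illustrated gap runs from about zero to 26 points and depends wholly on assumed non-compliance, UB share and confinement effect. This should be fixed because the remedy is cheap and the question cannot otherwise be answered from the planned output.

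ITT would not give a clean randomized comparison. This ITT set still requires one valid diary week, and Protocol 6.3 imputes nothing, so dropout is not cured. The documents also conflict on the design: the SAP says "This is an open-label, randomized, forced-switching study to be conducted at multiple study sites", Protocol 2.1 says "This is an open-label, non-randomized, forced-switching study to be conducted at multiple study sites", and the topography and PK subjects are assigned to VLN.

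**What to change.** 1. In SAP 7.3, 8.4 and 10.3, name the population for the mixed model. In 10.3 that paragraph also refers to biomarkers, although Tables 14.2.9.x.3 are for subjective effects.
2. Add ITT versions of Tables 14.2.1.1.3, 14.2.5.x.3 and 14.2.9.x.3 beside PP, each with estimate, interval and p-value. Do not rest the between-group conclusion on PP alone. Topography and PK are left out because those subjects are all on VLN.
3. Useful but optional: ITT paired tests for CPD (14.2.1.1.2) and Tneq (14.2.5.6.2, whose title in SAP 13.2 wrongly names 3-HPMA). PP may stay the lead set for the paired tests.

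**Cost.** SAP wording, extra tables and a second run of existing programs. Protocol 6 allows additional analyses in the SAP, so adding ITT beside PP needs no amendment. Tneq reductions may look smaller on ITT, and the CPD estimate may move either way or not at all.

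**Separate wording points.** SAP 7.3 labels both the paired and the between-group analysis primary, while Protocol 6.1.1 and SAP 4.1 make the between-group comparison secondary. These should be reconciled; if that changes the primary analysis materially, Protocol 6 calls for an amendment. SAP 5 should restate from the cited method whether CPD VLN is total or VLN-only, and which visit's ratio counts.
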